6.1 Screening

Screening examinations (Visit 1) are to include the procedures found in the [Assessment schedules](#) and should occur within 74-15 days prior to Day 1. The informed consent must be signed prior to ANY screening procedure being performed. Patients that do not meet eligibility criteria are allowed to be rescreened and should be given a new patient ID number. The rescreening should be documented in the source files.

6.2 Dietary, fluid and other restrictions

During recruitment, screening/informed consent review, and baseline visit, the patients will be informed and reminded of the following restrictions:

- Patient should maintain their normal exercise regime (i.e. no new strenuous physical exercise (e.g., weight training, aerobics, football) for 7 days before dosing until after Study Completion evaluation.
- Patients should report to the site at each visit in an 8 hour fasted state. During a PK profile, patients will be provided lunch 4 hours post-dose.

6.3 Patient demographics/other baseline characteristics

Demographics

Patient demographic and baseline characteristic data to be collected on all patients include: date of birth, sex, race, predominant ethnicity.

Relevant medical history / current medical conditions

Relevant medical history and current medical conditions will be recorded on the in the CRF until the start of the study drug.

Where possible, diagnoses and not symptoms will be recorded. Cushing's disease history together with the medication/treatment used will be collected.

Any event or change in the patient's condition or health status occurring **prior to** the initial study drug administration will be reported in the Relevant medical history/Current medical conditions section of the CRF.

6.4 Treatment exposure and compliance

Treatment compliance will be determined by collecting a trough plasma PK sample at the end of the last dose (C12hr) of each b.i.d. regimen, as detailed in [Section 6.7](#).

6.5 Efficacy / pharmacodynamic assessments

The following efficacy/pharmacodynamic assessments will be done using a central laboratory: UFC, plasma cortisol, plasma ACTH, salivary cortisol and aldosterone, 11-deoxycortisol, plasma and urine 11-deoxycorticosterone, plasma and urine aldosterone, plasma renin, PK, testosterone and estradiol, LH, FSH, IGF-1, urinary creatinine, urine sodium and potassium, insulin, HbA1c, TSH, free T4. Local labs can be used throughout the study for dose titrations and/or if a faster turnaround time is needed for safety reasons. Local values for UFC, plasma ACTH, plasma and urine deoxycorticosterone, testosterone and estradiol will be captured in the eCRF as applicable.

6.5.1 Mean urinary free cortisol and creatinine

The primary efficacy parameter will be urinary free cortisol. UFC will be measured in three 24-hour urine specimens collected within 7 days of day -7. The three samples will be averaged to obtain the baseline UFC level. Throughout the study, patients will collect three 24-hour urine specimens within 4 days prior to the next visit according to the [Assessment schedules](#). If at any time, the Patient's UFC is < ULN on 2 consecutive measurements dose escalation will be halted and the patient will remain on the current efficacious dose through week 10. During the two long term extension phases, (extension-1 and extension-2) patients will collect two 24-hour urine specimens within 7 days prior to the next visit. Urine creatinine levels will also be measured to ensure validity of the 24-hour collection.

6.5.1.1 Pharmacodynamic collection and processing

Procedures for sample handling and storage will be supplied by the local and central laboratories. All sampling should have application of unique sample numbering within the sample log table contained within [Appendix 1](#).

6.5.1.2 Pharmacodynamic analytical method(s)

Procedures for sample analysis will be supplied by the local and central laboratories and checked by Novartis personnel.

6.5.2 Plasma ACTH, plasma cortisol, 11-deoxycortisol and renin

Plasma ACTH, cortisol, 11-deoxycortisol and renin will be measured via blood samples taken at visits according to the [Assessment schedules](#).

6.5.2.1 Pharmacodynamic collection and processing

Procedures for sample handling and storage will be supplied by the central laboratory. All sampling should have application of unique sample numbering within the sample log table contained within the [Appendix 1](#).

6.5.2.2 Pharmacodynamic analytical method(s)

Procedures for sample analysis will be supplied by the central laboratory and checked by Novartis personnel.

6.5.3 Plasma and urine aldosterone and 11-deoxycorticosterone

Aldosterone and 11-deoxycorticosterone will be measured via blood and urine samples taken at visits according to the [Assessment schedules](#).

6.5.3.1 Pharmacodynamic collection and processing

Procedures for sample handling and storage will be supplied by the central laboratory. All sampling should have application of unique sample numbering within the sample log table contained within [Appendix 1](#).

6.5.3.2 Pharmacodynamic analytical method(s)

Procedures for sample analysis will be supplied by the central laboratory and checked by Novartis personnel.

6.5.4 Serum and urine sodium and potassium

Sodium and potassium will be measured via blood and urine samples taken at visits according to the [Assessment schedules](#).

6.5.4.1 Pharmacodynamic collection and processing

Serum sodium and potassium will be assessed as part of the clinical chemistry panel (see [Section 6.6.4.2](#) below) and will therefore be performed by the local lab. Procedures for sample handling and storage for urine will be supplied by the central laboratory. All sampling should have application of unique sample numbering within the sample log table contained within [Appendix 1](#).

6.5.4.2 Pharmacodynamic analytical method(s)

Procedures for urine sample analysis will be supplied by the central laboratory and checked by Novartis personnel.

6.5.5 Salivary cortisol and aldosterone

Cortisol and aldosterone will be measured via saliva samples taken at baseline and weekly thereafter until Day 154. From Day 154 through Day 322 it will be collected every 28 days (Day 182, D210, D238, D266, D294 and D322) and from Day 322 through 490 it will be collected every 3 months (D406 and D490). During long term extension-2 samples will be collected every 3 months during the first 18 months, and every 6 months thereafter. Patients will collect a morning and evening saliva sample (upon waking and just prior to bedtime e.g., 6-8:00 and 23-24:00 respectively)

6.5.5.1 Pharmacodynamic collection and processing

Procedures for sample handling and storage will be supplied by the central laboratory. All sampling should have application of unique sample numbering within the sample log table contained within [Appendix 1](#).

6.5.5.2 Pharmacodynamic analytical method(s)

Procedures for sample analysis will be supplied by the central laboratory and checked by Novartis personnel.

6.5.6 Other pharmacodynamic laboratory evaluations

Insulin will be measured via blood samples taken at visits according to the [Assessment schedules](#). HbA_{1c}, IGF-1, TSH, free T4, LH, FSH will be collected at visits according to the Assessment schedules. Testosterone and estradiol will be collected at visits according to the Assessment schedules.

6.5.6.1 Pharmacodynamic collection and processing

Procedures for sample handling and storage will be supplied by the central laboratory. All sampling should have application of unique sample numbering within the sample log table contained within [Appendix 1](#).

6.5.6.2 Pharmacodynamic analytical method(s)

Procedures for sample analysis will be supplied by the central laboratory and checked by Novartis personnel.

6.6 Safety

6.6.1 Physical examination

A complete physical examination will include the examination of general appearance, skin, neck (including thyroid), eyes, ears, nose, throat, lungs, heart, abdomen, back, lymph nodes, and extremities, vascular and neurological. If indicated based on medical history and/or symptoms, rectal, external genitalia, breast, and/or pelvic exams may be performed. This will be conducted at visits according to the [Assessment schedules](#).

Information for all physical examinations must be included in the source documentation at the study site and will not be recorded the (e)CRF. Significant findings that are present prior to the start of study drug must be included in the Relevant Medical History/Current Medical Conditions screen on the patient's (e)CRF. Significant findings made after the start of study drug which meet the definition of an Adverse Event must be recorded on the Adverse Event screen of the patient's (e)CRF.

6.6.2 Vital signs

Vital signs include body temperature, BP and pulse measurements. After the patient has been sitting for 3 minutes, with back supported and both feet placed on the floor, systolic and diastolic blood pressure will be measured three times using an automated validated device, with an appropriately sized cuff. In case the cuff sizes available are not large enough for the patient's arm circumference, a sphygmomanometer with an appropriately sized cuff may be used.

Body temperature will be measured at visits according to the [Assessment schedules](#). Blood pressure and pulse rate will be measured at visits according to the Assessment schedules. If

vital signs are out-of-range at screening or baseline, the Investigator should obtain two additional readings, so that a total of five (5) consecutive assessments are made, with the patient seated quietly for approximately five (5) minutes preceding each repeat assessment. **At least the last reading must be within the ranges provided above in order for the patient to qualify.**

6.6.3 Height and weight

Height in centimeters (cm) and body weight (to the nearest 0.1 kilogram [kg] in indoor clothing, but without shoes) will be measured. Body height will be measured at screening and body weight will be measured at visits according to the Assessment schedules.

6.6.4 Laboratory evaluations

In the case where a laboratory assessment that is listed in the inclusion/exclusion criteria is outside of a **protocol-specified range** at screening and/or at the initial baseline, the assessment may be repeated once (for the purpose of inclusion), and in any case, prior to enrollment, to rule out laboratory error. If the repeat value remains outside of protocol-specified ranges, the patient should be excluded from the study.

The following laboratory evaluations for safety will be performed locally: hematology, clinical chemistry, urinalysis ([Section 6.6.4.1](#) to [Section 6.6.4.3](#)).

In the case where a laboratory range is **not specified by the protocol**, but is outside the reference range for the center at screening and/or initial baseline, a decision regarding whether the result is of clinical significance or not shall be made by the Investigator and shall be based, in part, upon the nature and degree of the observed abnormality. The assessment may be repeated once (for the purpose of inclusion) and in any case, prior to enrollment/randomization, to rule out laboratory error.

In all cases, the Investigator must document in the source documents, the clinical considerations (i.e., result was/was not clinically significant and/or medically relevant) in allowing or disallowing the patient to continue in the study.

Clinically relevant deviations of laboratory test results occurring during or at completion of the study must be reported and discussed with Novartis personnel. The results should be evaluated for criteria defining an adverse event and reported as such if the criteria are met. Repeated evaluations are mandatory until normalization of the result(s) or until the change is no longer clinically relevant. In case of doubt, Novartis personnel should again be contacted.

6.6.4.1 Hematology

Hemoglobin, hematocrit, red blood cell count, white blood cell count with differential, (monocytes, eosinophils, basophils, neutrophils, lymphocytes), and platelet count will be measured.

6.6.4.2 Clinical chemistry

Albumin, alkaline phosphatase, total bilirubin, bicarbonate/CO₂, calcium, total cholesterol, HDL-cholesterol, LDL-cholesterol, triglycerides, chloride, creatinine, CK, γ -GT, fasting

plasma glucose, LDH, inorganic phosphorus, lipase, amylase, magnesium, potassium, total protein, AST, ALT, sodium, urea/BUN and uric acid.

If the total bilirubin concentration is increased above 1.5 times the upper limit of normal, direct and indirect reacting bilirubin should be differentiated.

6.6.4.3 Urinalysis

A midstream urine sample (approx 30 mL) will be obtained, in order to avoid contamination with epithelial cells and sediments, and allow proper assessments.

A semi-quantitative "dipstick" evaluation for the following parameters will be performed: specific gravity, pH, glucose, protein, bilirubin, ketones, leukocytes and blood.

6.6.5 Electrocardiogram (ECG)

Cardiac monitoring will include 12-lead Safety ECGs, which are the primary assessment of safety at study visits, and 24-hour continuous 12-lead Holter recordings, which provide large amounts of additional ECG data with central reading, but are not intended to provide real-time assessment of cardiac intervals and cardiac rhythm.

Twenty-four hour continuous 12-lead Holter recording with central reading of data are done on each patient according to the [Assessment schedules](#).

Twelve-lead safety ECGs are collected at the study sites according to the [Assessment schedules](#). At each visit when a study drug dose is administered, the safety ECG should be collected at 1.5 hours post-dose (approximately at the time of C_{max}). If the patient chooses to enroll in long term extension-1 and long term extension-2 studies, 12-lead safety ECGs will also be done according to the [Assessment schedules](#), and the timing will also be 1.5 hours post-dose if study drug is administered.

Twelve-lead safety ECGs are collected at the study site using local ECG equipment. This ECG must be read on site by a qualified physician (e.g., the investigator, or another qualified physician such as a consulting cardiologist) at the time they are collected and documented on the ECG section of the CRF / eCRF.

Each 12-lead Safety ECG tracing should be labeled with the:

- study number
- patient initials
- patient number
- date and time

and kept in the source documents at the study site. The clock on the ECG machine should be synchronized with the central clock on a daily basis.

The eCRF will contain:

- date and time of ECG
- heart rate
- PR interval
- QT and QTc interval

- QRS duration

The Fridericia QT formula (QTcF) to correct for variations in heart rate should be used for clinical decisions ([Fridericia 1920](#)).

The purpose of the safety ECG is to identify patients with clinically significant (“notable”) ECG abnormalities. On the day of the first study drug administration (day 1), the pre-dose ECG must be done in triplicate. The mean of the QTcF from these 3 tracings is used as the baseline QTcF to be compared with the 1.5 hour post-dose ECG on Day 1 only.

Only ECGs with clinically significant (“notable”) abnormalities should be reported on the ECG tracing. A “notable abnormality” is defined as:

- Day 1 only: an increase in QTcF > 30msec at 1.5 hours post-dose, compared to the mean pre-dose baseline QTcF from the same day
- QTcF > 480msec with acute cardiovascular risk, as assessed by a consulting cardiologist
- Any QTcF > 500msec, confirmed by a consulting cardiologist

Notable ECG abnormalities should be recorded on the Adverse Events e(CRF) page. The overall interpretation will be collected with a Yes/No statement to confirm if any clinically significant abnormalities are present which need to be specified further.

For any ECGs with patient safety concerns, two additional 12-lead ECGs should be performed to confirm the safety finding. If there is a notable abnormality, then a cardiology consult should be called, and the Novartis Medical Monitor for this trial notified of the event.

ECGs must be recorded after 10 minutes rest in the supine position to ensure a stable baseline. The preferred sequence of cardiovascular data collection during study visits is ECG collection first, followed by vital signs, and then blood sampling for LCI699 pharmacokinetic (PK) assessment ([Figure 6-1](#)).

Figure 6-1 Sequence of cardiovascular data collection

Original ECG tracings, appropriately signed, will be archived at study site.

QT prolongation monitoring

On the day of the first administration of LCI699 (day 1), the pre-dose baseline ECG must be done in triplicate. The mean of the QTcF values from these three ECG tracings is used to determine the mean baseline QTcF for that day only. If the safety ECG (1.5 hours post-first dose of LCI) shows an increase in QTcF > 30ms from the mean baseline value, or the QTcF is > 480ms, then the patient should be discontinued from study drug. Any ECG in doubt

should be reviewed promptly by a consulting cardiologist before discontinuing the patient from LCI699 therapy.

If at any follow up visit, a QTcF > 500msec is observed on the 1.5 hour post-dose safety ECG, then triplicate ECGs, each 2-3 minutes apart, need to be taken after the initial ECG. The mean QTcF from the triplicate ECGs will be determined. If the mean QTcF is > 500msec, the patient has to interrupt study treatment while an urgent cardiology consultation is obtained to re-evaluate the ECG and perform a clinical consultation. If immediate treatment is required for patient safety, this should be initiated at the study site without delay and without waiting for confirmation by a cardiologist.

If the cardiologist confirms a mean QTcF > 500msec, the patient has to discontinue according to the discontinuation procedure described in [Section 5.5.9](#). The patient must remain under observation until the QTcF is < 480msec and serum electrolytes, calcium, and magnesium are measured and the results normal. This observation may be done at the site, in an Emergency Room, or a cardiology clinic, as appropriate and depending upon local resources.

Otherwise, and if the cardiologist confirms, that at least one ECG shows a QTcF > 480msec, the cardiac assessments described for a confirmed QTcF > 480msec need to be followed.

[figure not shown]
If at any follow up visit a $480\text{msec} < \text{QTcF} \leq 500\text{msec}$ is observed on the 1.5 hour post-dose safety ECG, the following steps need to be taken (described in [Figure 6-2](#)):

The patient has to interrupt study treatment while an urgent cardiology consultation is obtained to re-evaluate the ECG. If immediate treatment is required for patient safety this should be initiated at the study site without delay and without waiting for confirmation by a cardiologist.

- If a QTcF > 480msec is NOT confirmed, no further action needs to be taken;
- If a QTcF > 480msec is confirmed, a cardiologist must perform a thorough clinical evaluation to assess the patient for acute cardiovascular risk, and for possible underlying heart disease that needs additional evaluation and management.
 - a. If based upon the assessment by the cardiologist, the investigator considers that there is an acute cardiovascular safety risk and that the subject should not continue with study medication, the subject needs to be discontinued immediately (discontinuation criteria described in [Section 5.5.9](#)).
 - b. If based upon the assessment by the cardiologist, the investigator considers that there is not an acute cardiovascular safety risk, the subject can continue to receive study medication.

The patient must remain under observation until the QTcF is < 480msec and serum electrolytes, calcium, and magnesium are measured and the results are normal. This observation may be done at the site, in an Emergency Room, or a cardiology clinic, as appropriate and depending upon local resources. The results of the ECGs, cardiac examination and the recommendation by the cardiologist must be evaluated by the investigator to determine whether the subject should continue in the trial or not.

Figure 6-2 QT Prolongation Monitoring Flow Chart

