If UFC > ULN, the site will contact the patient to plan an interim escalation dose visit 7 days after the regular visit (on Day 21). At the interim visit, the patient will take the first escalated dose at the site, and remain for 1.5 hours in order to have a 12-lead Safety ECG. This ECG must be read on site by a qualified physician (e.g., the investigator, or another qualified physician such as a consulting cardiologist), who will decide whether or not there is a “notable abnormality”. Notable abnormality is defined as QTcF > 480msec with acute cardiac risk, QTcF > 500msec, or increase in QTcF > 60msec from baseline QTcF from the pre-dose ECG taken on the day of the first study drug administration (Day 1). If there is no notable abnormality, then the patient will be sent home to continue the higher dose until the next visit on the current schedule. If there is a “notable abnormality,” then a cardiology consult should be called, and the Novartis “Medical Monitor” for this trial notified of the event.

This schedule of events will continue every 2 weeks (i.e. Day 28, 42, 56) with potential interim dose escalation visits (on Days 35, 49, 63) during the dose escalation period, with the dose of LCI699 increasing according to [Figure 3-1](#). If at any time, the patients UFC is < ULN, dose escalation will be halted and the patient will remain on the current, efficacious dose through the rest of the dose escalation period (Week 10), and if UFC remains normal, continue until Week 22. Monitoring of UFC responses will continue every 2 weeks to allow additional dose adjustments if necessary. Accordingly, only a predose PK sample will be required for patients that remain on the efficacious dose. If at any time the patient experiences side effects which are either intolerable or meet dose adjustment criteria, the prescribed dose will be adjusted as outlined in [Section 5.5.4](#).

Between days 66-69, patients will perform three 24-hour urine collections. Patients will bring in their urine collection bottles to the site on Day 70 \pm 2 days. A pre-dose PK sample only (12 hr post previous PM dose) will be collected for patients on their previous maintained dose (<30 mg bid). Pre-dose (12 hr post previous PM dose), 1, 1.5, 2, 4 and 6 hour PK samples will be collected for patients receiving 30 mg bid. Patients will undergo safety/PD assessments at the site on Day 70 \pm 2 days.

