5.5.11 Discontinuation of study treatment

Patients may voluntarily discontinue from the study treatment for any reason at any time. If a patient decides to discontinue from the study treatment, the investigator should make a reasonable effort (e.g. telephone, email, letter) to determine the primary reason for this decision and record this information in the patient's chart and on the appropriate CRF pages. They may be considered withdrawn if they state an intention to withdraw, fail to return for visits, or become lost to follow-up for any other reason.

The investigator should discontinue study treatment for a given patient if he/she believes that continuation would be detrimental to the patient's well-being.

Study treatment must be discontinued under the following circumstances and according to Investigator discretion:

- Withdrawal of informed consent.
- Emergence of the following adverse events (compound specific):
 - hypertension defined as office mean sitting systolic BP > 180 mmHg or mean sitting diastolic BP > 110 mmHg (confirmed and persistent*).
- Any of the following laboratory abnormalities:
 - hyperkalemia (serum potassium > 5.5 mmol/L; confirmed and persistent*).
 - hypokalemia (serum potassium < 3.5 mmol/L; confirmed and persistent*).
 - hyponatremia (serum sodium < 130 mmol/L; confirmed and persistent*).
- QTcF > 500 msec, if confirmed by a cardiologist (see [Section 6.6.5](#)).
- QTcF > 480 msec, if the investigator determines it is no longer safe for the patient to continue in the study, based on ECGs, cardiac examination, and recommendation from a cardiologist (see [Section 6.6.5](#)).
- Pregnancy.
- Use of any other therapy for Cushing's disease.
- Any other protocol deviation that results in a significant risk to the patient's safety.

* Persistent is defined as unresolved with LCI699 dose or other concomitant medication changes

Patients who discontinue study treatment should NOT be considered withdrawn from the study. They should return for the assessments indicated in [Section 6](#). If they fail to return to return for these assessments for unknown reasons, reasonable effort (e.g. telephone, email, letter) should be made to contact them as specified in [Section 5.5.13](#).

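### Protocol Sections 3.1, 5.5.11 and 6.6.5 disagree on which QTcF change is notable at the interim escalation visits and on which Day 1 QTcF leads to discontinuation

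*Protocol*

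**What the plan says.** Three protocol sections set QTcF rules.

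- **Section 3.1**, in the instructions for the interim escalation visits: "Notable abnormality is defined as QTcF > 480msec with acute cardiac risk, QTcF > 500msec", or an "increase in QTcF > 60msec from baseline QTcF from the pre-dose ECG" of Day 1. A qualified physician reads the tracing on site and decides. The decision has a direct consequence: "If there is no notable abnormality, then the patient will be sent home to continue the higher dose". If the tracing is notable, a cardiology consult is called and the sponsor's medical monitor is told.
- **Section 6.6.5**, which covers all safety ECGs, has its own list of notable abnormalities. The first item is "Day 1 only: an increase in QTcF > 30msec at 1.5 hours post-dose, compared to the mean pre-dose baseline QTcF from the same day". The other two are QTcF above 480 msec with acute risk as judged by a consulting cardiologist, and QTcF above 500 msec confirmed by one. The mean of the Day 1 triplicate "is used as the baseline QTcF to be compared with the 1.5 hour post-dose ECG on Day 1 only". Notable ECGs go on the adverse event page. For the first-dose ECG, the section adds that if the rise exceeds 30 msec, "or the QTcF is > 480ms, then the patient should be discontinued from study drug". Tracings in doubt go to a cardiologist first.
- **Section 5.5.11** lists the reasons for stopping study treatment. Its two QTcF entries are above 500 msec confirmed by a cardiologist, and "QTcF > 480 msec, if the investigator determines it is no longer safe for the patient to continue in the study". Both refer to Section 6.6.5. No change-from-baseline rule is listed.

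**The concern.** At an interim visit, the word notable separates a patient who goes home on the higher dose from one who is referred to cardiology and reported to the sponsor. On Day 1, the discontinuation rule decides whether treatment continues at all. If two sections give different answers for one tracing, sites that each follow the protocol can act differently. The adverse event record can differ too, because Section 6.6.5 sends notable ECGs to the adverse event page. ECG monitoring was intensified in this study because of a possible QT effect, so these rules need to be unambiguous.

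**Working it through.** The plan gives no figure to reproduce. The check sets the rules side by side and applies them to assumed ECG values.

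**Notable abnormality at the interim visits**

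| Element | Section 3.1 | Section 6.6.5 |
|---|---|---|
| Change criterion after Day 1 | rise above 60 msec | none in the text |
| Use of Day 1 baseline | applied at interim visits | Day 1 comparison only |
| Above 480 msec | with acute risk; on-site physician decides | acute risk assessed by consulting cardiologist |
| Above 500 msec | no confirmation stated | confirmed by consulting cardiologist |
| Adverse event entry | not mentioned | required if notable |

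- *Day 21, 400 to 465 msec.* The rise is 465 − 400 = 65, above 60, so the tracing is notable under Section 3.1. Under Section 6.6.5, 465 is below 480, and the Day 1 baseline may not be used, so it is not notable.
- *Interim visit, 465 to 505 msec, not confirmed by a cardiologist.* The rise is 40, below 60, but 505 exceeds 500, so it is notable under Section 3.1. It is not notable under Section 6.6.5 without confirmation. Section 6.6.5 has its own repeat-ECG steps above 500 msec, so this difference concerns classification and adverse event entry, not whether the tracing is followed up.

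**Discontinuation on Day 1**

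- *400 to 435 msec.* The rise is 35, above 30. Section 6.6.5 says the patient should be discontinued. No QTcF entry in Section 5.5.11 is met.
- *465 to 485 msec, no acute risk.* The rise is 20, below 30, but 485 exceeds 480. Section 6.6.5 says discontinue. Section 5.5.11 does so only if the investigator judges it unsafe to continue. The tracing is also absent from Section 6.6.5's own notable list. A baseline of 465 is possible at entry, because exclusion criterion 22 applies only above 470 msec.

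**Discontinuation at follow-up visits**

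- 490 msec confirmed, with acute risk: Sections 5.5.11 and 6.6.5 both lead to discontinuation.
- 490 msec confirmed, without acute risk: both allow treatment to continue.
- 505 msec confirmed: both lead to discontinuation.

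**Cross-reference.** Section 6.6.5 twice refers to Section 5.5.9 for discontinuation. In the current text, 5.5.9 is Prohibited treatment and the criteria are in 5.5.11.

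**SAP.** Section 7.5.4 derives QTcF from QT and heart rate, and flags rises above 30 and above 60 msec at any post-baseline time. The Day 21 example, at 65, exceeds both, whichever protocol section the site followed.

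**The case against.** A reader might infer four stronger conclusions that the documents do not support.

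- *That the 30 and 60 msec thresholds contradict each other.* They do not. The first applies on Day 1 and the second at interim visits from Day 21, so they never meet on one tracing.
- *That every later ECG visit is affected.* Section 3.1 gives its definition only within the interim-visit instructions, and those visits occur only when UFC is above the ULN. From Day 70 onward, Section 6.6.5 is the only source of a definition.
- *That Sections 5.5.11 and 6.6.5 disagree throughout.* Section 5.5.11 cites Section 6.6.5 and allows investigator discretion, and the two agree at follow-up visits. The missing 30 msec rule can be read as silence rather than contradiction. Section 6.6.5 itself says should, and has doubtful tracings reviewed first. This does not explain why a Day 1 QTcF above 480 msec is unconditional in one section and a matter of judgement in the other.
- *That the reported QT results are compromised.* The SAP flags use recorded intervals and do not depend on site classification. Aligning them with the protocol's definition would be a preference, not a correction.

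The adverse event effect is also indirect. Section 3.1 gives no recording instruction, and Section 7.1 separately makes any clinically significant test result an adverse event.

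The strongest point is timing. By March 2014, 17 of the 19 patients enrolled under Amendment 4 had completed the core phase and 2 had discontinued. The 10 still on treatment in May 2018 were past Day 1 and the interim visits. The completed thorough QT study is also reported as below the level of regulatory concern. This limits the present effect, but the contradiction remains in the current text.

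**Conclusion.** The concern holds on two points. At up to four interim visits, Section 3.1 applies a 60 msec change criterion and an on-site decision, whereas Section 6.6.5 omits that criterion, bars that use of the Day 1 baseline and requires a cardiologist. On Day 1, Sections 6.6.5 and 5.5.11 treat a QTcF above 480 msec differently, and only Section 6.6.5 has the 30 msec rule.

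The number of patients or adverse event entries affected cannot be computed, because the documents give no QTcF distribution at these visits. The ECG values above are illustrations. The comparison rests on the protocol text; the QT flow chart (Figure 6-2) was not available and might add detail.

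**What to change.** Reconcile Sections 3.1, 5.5.11 and 6.6.5 to:

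- one definition of a notable QTcF abnormality, stating the baseline, the visits where it applies and who confirms it;
- one list of QTcF discontinuation criteria, covering Day 1 explicitly;
- a corrected reference in Section 6.6.5, from 5.5.9 to 5.5.11.

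Which thresholds apply is for the sponsor's clinical team. No SAP change is needed. The cost is protocol wording only, with no new assessments.
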